**Table 8-1 Futility Assessment: Information Fractions and Futility Boundaries**

Look #	Information Fraction	Sample Size	Futility Boundary		Incremental Boundary Crossing Probabilities	
			Response Rate	Responder (n)	Under H0: $\pi = 0.1$	Under H1: $\pi = 0.2$
1	0.167	25	0	1	0	0
2	0.333	50	0.035	2	0.064	0.002
3	0.500	75	0.093	7	0.357	0.009
4	0.667	100	0.121	13	0.340	0.017
5	0.833	125	0.137	18	0.160	0.021

Note: The information fractions and futility boundaries are based on a sample size of 150 patients.

The information boundaries based on sample sizes of 250, 200 and 50 patients are outlined in [Table 8-2](#), [Table 8-3](#), and [Table 8-4](#), respectively. For each look, if the number of responders specified under the futility boundary is observed, enrollment will proceed without interruption.

**Table 8-2 Futility Assessment for a sample size of 250**

Look #	Information Fraction	Sample Size	Futility Boundary		Incremental Boundary Crossing Probabilities	
			Response Rate	Responder (n)	Under H0: $\pi = 0.1$	Under H1: $\pi = 0.2$
1	0.1	25	0.000	1	0.000	0.000
2	0.2	50	0.000	1	0.000	0.000
3	0.3	75	0.000	1	0.000	0.000
4	0.4	100	0.040	5	0.021	0.000

Look #	Information Fraction	Sample Size	Futility Boundary		Incremental Boundary Crossing Probabilities	
			Response Rate	Responder (n)	Under H0: $\pi = 0.1$	Under H1: $\pi = 0.2$
5	0.5	125	0.072	10	0.131	0.000
6	0.6	150	0.094	15	0.256	0.000
7	0.7	175	0.110	20	0.259	0.001
8	0.8	200	0.121	25	0.176	0.002
9	0.9	225	0.130	30	0.092	0.002

**Table 8-3 Futility Assessment for a sample size of 200**

Look #	Information Fraction	Sample Size	Futility Boundary		Incremental Boundary Crossing Probabilities	
			Response Rate	Responder (n)	Under H0: $\pi = 0.1$	Under H1: $\pi = 0.2$
1	0.125	25	0.000	1	0.000	0.000
2	0.25	50	0.000	1	0.000	0.000
3	0.375	75	0.039	3	0.039	0.000
4	0.5	100	0.081	9	0.222	0.001
5	0.625	125	0.105	14	0.320	0.003
6	0.75	150	0.122	19	0.232	0.005
7	0.875	175	0.133	24	0.116	0.007

**Table 8-4 Futility Assessment for a sample size of 50**

Look #	Information Fraction	Sample Size	Futility Boundary		Incremental Boundary Crossing Probabilities	
			Response Rate	Responder (n)	Under H0: $\pi = 0.1$	Under H1: $\pi = 0.2$
1	0.5	25	0.156	4	0.827	0.293

**8.5 Statistical Methods****8.5.1 Demographics and Baseline Characteristics**

Descriptive summaries of demographic and baseline characteristics for all enrolled patients will be tabulated. Patients will be tabulated by tumor indication.

**8.5.2 Safety Analyses**

Safety will be assessed by clinical review of all relevant parameters including AEs, SAEs, laboratory values, vital signs, ECG results, concomitant medications, and thyroid function.

Unless specified otherwise, the safety analyses will be conducted for the safety population defined in Section 8.2.1. The results of these analyses will be presented by tumor indication.

Summary tables and listings will be provided for all reported TEAEs, defined as AEs that start on or after the first administration of study drug. The reported AE term will be assigned standardized coding using MedDRA; the MedDRA version shall be specified in study documents, including but not limited to the coding plan and data management plan.

TEAEs will be summarized based on the number and percentage of patients experiencing the event by MedDRA System Organ Class and preferred term. The causal relationship between the occurrence of an AE and study drug will be judged by the Investigator based on the conventions described in Section 9.3. In the event a patient experiences repeat episodes of the same AE, then the event with the highest severity grade and strongest causal relationship to study drug will be used for purposes of incidence tabulations.

Tabular summaries will be provided for:

- All TEAEs.
- TEAEs by relationship (yes, no) to underlying disease, other medical conditions, or concomitant medications, and maximum severity grade.
- TEAEs with action of study drug delayed/interrupted or treatment reduced.
- TEAEs with action of study drug discontinued.
- All SAEs.
- SAEs by relationship (yes, no) to underlying disease, other medical conditions or concomitant medications.
- SAEs with action of study drug delayed/interrupted or treatment reduced.

The observed DLT rate in each dose cohort will be calculated by the crude proportion of patients who experience DLT. Multiple concurrent AEs leading to DLT will be considered a single DLT. The estimate of the DLT rate will be accompanied by a 2-sided 95% exact binomial CI.

All deaths, including on-study deaths, that occur within 28 days of treatment discontinuation will be reported in a patient listing, which will include the primary cause of death and the number of days between the date of the last dose of study drug and death. For patients undergoing LTFU, the duration of survival following the initiation of study drug will be summarized in a descriptive manner using the Kaplan-Meier method. A summary of the anticancer therapies received after discontinuation of study drug will be provided.

Hematology and serum chemistries will be summarized in a descriptive manner by calculating the mean, standard deviation, median, and range, as follows:

- Baseline value
- Minimum post-baseline value

- Maximum post-baseline value
- Average post-baseline value
- Last post-baseline value.

Laboratory values will be assigned toxicity grades when available using the NCI CTCAE, version 4.03. Directional shifts in laboratory toxicity grades (comparing baseline grade with worst post-baseline grade) will be analyzed using standard shift tables, presenting number and proportion of patients and their maximum grade shift. For analytes without a toxicity grading scale, the shift table will present directional shifts from baseline to above or below the laboratory standard normal range using the maximum increase and/or decrease observed throughout the course of treatment/observation.

All patients will have pre-treatment baseline vital signs and pre-dose measurements on D1 of each cycle. The results for each vital sign will be summarized in a descriptive manner by calculating the mean, standard deviation, median, and range by time point in the same manner described for laboratory values. For these analyses, the minimum, maximum, average, and last post-baseline value will be determined relative to the baseline vital sign measurements only. In addition, serial vital signs measurements will be obtained pre- and post-dose on the first day of each patient's selpercatinib treatment in conjunction with serial PK sampling. For each patient, the vital signs change from the pre-dose value will be summarized in a descriptive manner. The Wilcoxon signed rank test may be used to assist in the identification of any systematic changes.

Prior and concomitant medications will be coded using the World Health Organization Drug (WHO Drug) Dictionary; the WHO Drug version shall be specified in study documents, including but not limited to the study coding plan and data management plan.

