### **6.4      *Removal of Patients from Therapy or Assessment***

Patients will be advised that they are free to discontinue study treatment at any time and that they will be followed for survival after discontinuing treatment (see Section 7.7). Over the course of the study, the Investigator and/or the Sponsor should remove a patient from treatment for any of the reasons listed below:

- PD  
**Exception:** Patients with documented PD who are tolerating treatment and, in the opinion of the Investigator, are deriving clinical benefit from continuing study treatment, may continue treatment with prior Sponsor approval. Sponsor approval is not required for continuing selpercatinib treatment upon a subsequent progression, provided that continued benefit to the patient is documented.
- Unacceptable toxicity
- Intercurrent illness compromising ability to fulfill protocol requirements
- Pregnancy

- Requirement for alternative treatment in the opinion of the Investigator, unless such treatment is temporary (e.g., local radiation or surgery for disease that does not meet the definition of PD)
- Significant noncompliance with protocol
- Withdrawal of consent by the patient
- Loss to follow-up
- Death
- Study terminated by Sponsor

At the time a patient discontinues treatment, all safety data normally required at the EOT visit will be obtained if possible, as outlined in Section 7.5. Patients will enter LTFU where they may be required to undergo disease assessments (see Section 7.7).

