## **7.7 Long-Term Follow-Up**

After treatment discontinuation, LTFU will occur approximately every 3 months ( $\pm 1$  month) until the patient has withdrawn consent for further participation, is lost to follow-up, has died, or the Sponsor makes a decision to close the study. Assessments may include: subsequent anticancer therapy(ies) and survival status. LTFU may be conducted by phone. For any patient who is lost to follow-up, the study site will attempt to ascertain survival information via public database search. If survival status still cannot be ascertained, patients will be considered lost to follow-up and will be censored appropriately.

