### **8.5.3      *Efficacy Analyses***

The efficacy analyses will be conducted on the Safety Analysis Set of patients with at least 6 months of treatment from the first dose of selpercatinib. These analyses will be summarized per tumor indication, including patients from both the Phase 1 and Phase 2 portions. A Statistical Analysis Plan (SAP) will provide specific details on the efficacy analysis set.

ORR will be assessed using RECIST 1.1 ([Table 11-9](#)) or RANO ([Table 11-11](#), for patients with primary CNS tumors), as appropriate to tumor type. The estimate of the ORR will be calculated based on the maximum likelihood estimator (i.e., crude proportion of patients with best overall response of CR or PR that are confirmed based on RECIST 1.1 or RANO). The estimate of the ORR will be accompanied by 2-sided CIs with various coverage probabilities (e.g., 80%, 95%). The analysis of ORR will be conducted both by the responses determined by each Investigator and responses as determined by IRC.

Waterfall plots will be used to depict graphically the maximum decrease from baseline in the sum of longest diameters of target lesions.

DOR will be calculated for patients who achieve CR or PR. For such patients, DOR is defined as the number of months from the start date of CR or PR (whichever response status is observed first) and subsequently confirmed, to the first date that PD is objectively documented. If a patient dies, irrespective of cause, without documentation of PD beforehand, then the patient's date of death will be used to denote the response end date.

PFS will be derived for each patient as the number of months from the date of the first dose of study drug to the earlier of documented PD or death due to any cause. Patients who are alive and without documented PD as of a data analysis cutoff date will be right-censored according to the censoring methods described later in this section. Whenever appropriate, the same censoring methods will be used for DOR.

OS will be derived for each patient as the number of months from the date of the first dose of study drug to the date of death, irrespective of cause. Patients who are alive or lost to follow-up as of a data analysis cutoff date will be right-censored. The censoring date will be determined from the last date the patient was known to be alive or data analysis cutoff date, whichever occurs first.

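### Protocol 8.5.2 times survival from first dose but limits the curve to patients in long-term follow-up: a biased descriptive summary that should be deleted (minor)

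*Protocol*

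**What the plan says.** **The sentence.** Protocol 8.5.2 places it between the listing of deaths and the summary of anticancer therapies given after study drug: "For patients undergoing LTFU, the duration of survival following the initiation of study drug will be summarized", descriptively, with Kaplan-Meier as the method. The default population for that section is the Safety Analysis Set: "Unless specified otherwise, the safety analyses will be conducted for the safety population defined in Section 8.2.1". The LTFU qualifier is such a specification.

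**When LTFU starts.** Protocol 7.7: "After treatment discontinuation, LTFU will occur approximately every 3 months". Protocol 6.4, on patients who stop treatment: "Patients will enter LTFU where they may be required to undergo disease assessments". Table 7-1, footnote e, counts LTFU from the last dose.

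**The OS endpoint.** Protocol 8.5.3: "OS will be derived for each patient as the number of months from the date of the first dose of study drug" to death from any cause. On censoring it adds: "Patients who are alive or lost to follow-up as of a data analysis cutoff date will be right-censored". It uses Kaplan-Meier with 95% confidence intervals. SAP 4.3.10 has the same origin, event and censoring principle, and no LTFU condition.

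**The SAP safety section.** SAP 4.3.11.3 reports deaths in a summary table and a patient listing. Nothing in SAP 4.3.11 plans a survival curve for LTFU patients. SAP 4.7 lists one change from the protocol: efficacy is analysed by indication rather than by cohort.

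**The concern.** The 8.5.2 summary selects patients by something that happens after baseline (stopping drug alive) but starts the clock at baseline. Three things follow from the literal wording:

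- Patients still on drug at cutoff are removed, where a survival analysis would censor them.
- Patients who die on drug never enter the set.
- For those who do enter, the interval from first dose to LTFU entry is immortal: they could not have died in it and still been counted. No landmark or left truncation is stated.

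Such a curve does not estimate survival in treated patients. At stake is whether the report could carry a second survival curve with the same origin, event and method as OS but a different and selected population. No test, decision or endpoint depends on it.

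**Working it through.** The documents give no survival rate, OS event count, time on drug or on-treatment death rate, so there is no plan figure to reproduce. The check compares the two texts and then uses an illustrative model to ask which way the bias runs.

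**1. Texts side by side**

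| | Protocol 8.5.2 sentence | Protocol 8.5.3 and SAP 4.3.10 |
|---|---|---|
| Origin | first dose | first dose |
| Event | death | death, any cause |
| Method | Kaplan-Meier | Kaplan-Meier |
| Patients | those in LTFU | no LTFU condition |
| Still on drug at cutoff | not in the set | right-censored |
| Death on treatment | not in the set | event |

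**2. Model (every input is an assumption)**

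Let D be time to stopping drug, X time to on-treatment death and P survival after stopping. All are exponential with rate ln 2 / median.

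- Death time T = X if X < D, otherwise D + P.
- Entry is uniform over 30 months; cutoff is at 36 or 60 months; censoring time C = cutoff - entry.
- LTFU set: D < X and D < C.
- Kaplan-Meier from first dose is applied to min(T, C), for all treated patients and for the LTFU set, with 200,000 patients per scenario.

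**3. Check of the model**

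For all treated patients, with rates a (stopping), b (on-treatment death) and c (death after stopping):

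S(t) = exp[-(a+b)t] + a/(a+b-c) × {exp(-ct) - exp[-(a+b)t]}

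With medians 18, 120 and 12 months and t = 24:

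- a + b = ln 2 × (1/18 + 1/120) = 0.04428, so exp[-(a+b)t] = 0.3455.
- exp(-ct) = 0.25.
- a/(a+b-c) = (20/360)/(-7/360) = -2.857.
- S(24) = 0.3455 + (-2.857)(0.25 - 0.3455) = 0.618.

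The simulation gives 0.615 (cutoff 36) and 0.618 (cutoff 60).

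**4. Results: 24-month survival**

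Medians are in the order D / X / P, in months. The shift is LTFU-only minus all treated, in percentage points.

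| Medians | Cutoff | Still on drug | On-treatment death | In LTFU set | All treated | LTFU only | Shift |
|---|---|---|---|---|---|---|---|
| 18/120/12 | 36 | 42.2% | 7.6% | 50.3% | 0.615 | 0.490 | -12.5 |
| 18/120/12 | 60 | 14.7% | 11.1% | 74.2% | 0.618 | 0.600 | -1.8 |
| 36/240/18 | 36 | 63.9% | 4.8% | 31.3% | 0.811 | 0.641 | -17.0 |
| 36/240/18 | 60 | 37.5% | 8.1% | 54.4% | 0.812 | 0.754 | -5.8 |
| 24/60/24 | 36 | 45.5% | 15.5% | 39.0% | 0.683 | 0.689 | +0.6 |
| 24/60/24 | 60 | 17.2% | 23.8% | 59.0% | 0.680 | 0.762 | +8.2 |
| 12/60/36 | 60 | 5.2% | 15.9% | 78.9% | 0.697 | 0.788 | +9.1 |
| 12/36/48 | 36 | 24.4% | 19.1% | 56.5% | 0.663 | 0.803 | +14.0 |
| 12/36/48 | 60 | 3.9% | 24.0% | 72.0% | 0.665 | 0.827 | +16.2 |

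**5. Reading**

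Removing patients still on drug pulls the curve down. Removing on-treatment deaths, with the immortal time that goes with it, pushes it up. The first dominates when many patients remain on drug at cutoff, the second when on-treatment deaths are frequent and follow-up is mature. They can also nearly cancel (24/60/24, cutoff 36).

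**The case against.** **The sentence may only say where the data come from.** Table 7-1 marks survival under LTFU alone, and the next sentence in 8.5.2 concerns therapies after discontinuation, which LTFU also collects. The protocol does not state that the restriction is exclusive. This is a fair reading and cannot be excluded. But the sentence stands in the analysis section and names a population, an origin and a method. If it means no more than OS, it duplicates 8.5.3 with a misleading qualifier. The same edit serves either reading.

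**OS is correctly defined elsewhere.** This stands in full. A reader might infer that the trial's OS result drops patients on drug and on-treatment deaths. It does not: 8.5.3 and SAP 4.3.10 carry no LTFU condition.

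**On-treatment deaths are reported.** This also stands. They appear in the 8.5.2 listing and in the SAP 4.3.11.3 table and listing. Reporting them there does not put them in the curve.

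**The SAP governs and has no such curve.** Protocol Section 8 leaves methods and displays to the SAP, and the current SAP was written for the final study report. So it would go too far to say that a conflicting curve will appear beside OS. What remains is that SAP 4.7 does not record the sentence as dropped.

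**Tempting inference on direction.** Because time on drug may be long, a reader might conclude that the curve understates survival. The documents give neither time on drug nor the on-treatment death rate, and plausible inputs produce either sign.

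**Conclusion.** As written, the 8.5.2 summary is a biased estimate of survival in treated patients. That conclusion rests on the literal wording and on LTFU starting after treatment ends; it does not depend on the simulation. The simulated range of about -17 to +16 percentage points at 24 months rests wholly on assumed exponential times, accrual and cutoffs. It shows that the bias can be material in either direction, and it is not an estimate for this trial.

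Severity is minor: this is a descriptive safety sentence, the primary endpoint and OS are untouched, and the SAP does not carry the curve forward.

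**What to change.** 1. Delete the sentence from Protocol 8.5.2, or replace it with a cross-reference to OS as defined in Protocol 8.5.3 and SAP 4.3.10. The replacement should not say that those analyses use the full Safety Analysis Set: 8.5.3 confines efficacy analyses to patients with at least 6 months of treatment, and SAP 2.2 asks for at least 6 months of potential follow-up (or earlier progression or death).
2. Add a line to SAP 4.7 that the LTFU-only survival curve is not performed.
3. If survival after treatment is of interest, time it from treatment discontinuation or from LTFU entry.
4. Keep the summary of subsequent anticancer therapies.

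The cost is one protocol sentence and one SAP line, with no new data. SAP 4.1 requires an amendment only when a principal feature of the protocol changes; other changes to the analysis methods are described and justified in the study report. The protocol edit can therefore wait for the next amendment if the SAP note is made now.

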### **8.5.3      *Efficacy Analyses***

The efficacy analyses will be conducted on the Safety Analysis Set of patients with at least 6 months of treatment from the first dose of selpercatinib. These analyses will be summarized per tumor indication, including patients from both the Phase 1 and Phase 2 portions. A Statistical Analysis Plan (SAP) will provide specific details on the efficacy analysis set.

ORR will be assessed using RECIST 1.1 ([Table 11-9](#)) or RANO ([Table 11-11](#), for patients with primary CNS tumors), as appropriate to tumor type. The estimate of the ORR will be calculated based on the maximum likelihood estimator (i.e., crude proportion of patients with best overall response of CR or PR that are confirmed based on RECIST 1.1 or RANO). The estimate of the ORR will be accompanied by 2-sided CIs with various coverage probabilities (e.g., 80%, 95%). The analysis of ORR will be conducted both by the responses determined by each Investigator and responses as determined by IRC.

Waterfall plots will be used to depict graphically the maximum decrease from baseline in the sum of longest diameters of target lesions.

DOR will be calculated for patients who achieve CR or PR. For such patients, DOR is defined as the number of months from the start date of CR or PR (whichever response status is observed first) and subsequently confirmed, to the first date that PD is objectively documented. If a patient dies, irrespective of cause, without documentation of PD beforehand, then the patient's date of death will be used to denote the response end date.

PFS will be derived for each patient as the number of months from the date of the first dose of study drug to the earlier of documented PD or death due to any cause. Patients who are alive and without documented PD as of a data analysis cutoff date will be right-censored according to the censoring methods described later in this section. Whenever appropriate, the same censoring methods will be used for DOR.

OS will be derived for each patient as the number of months from the date of the first dose of study drug to the date of death, irrespective of cause. Patients who are alive or lost to follow-up as of a data analysis cutoff date will be right-censored. The censoring date will be determined from the last date the patient was known to be alive or data analysis cutoff date, whichever occurs first.

DOR, PFS, and OS will be summarized descriptively using the Kaplan-Meier method with 95% CIs. Median follow-up for each endpoint will be estimated according to the Kaplan-Meier estimate of potential follow-up ([Schemper and Smith 1996](#)).

For patients who meet one or more of the following conditions, DOR and PFS will be right-censored as appropriate:

- Patients with no baseline or post-baseline disease assessments unless death occurred prior to the first planned post-baseline assessment (in which case the death will be considered a PFS event)
- Patients who initiate subsequent anticancer therapy in the absence of documented PD
- Patients who die or have PD after missing 2 or more consecutively scheduled disease assessment visits
- Patients who are last known to be alive and without documented PD on or before the data cut-off date

For such patients, the progression or censoring date will be determined based on described conventions ([U.S.-Food-and-Drug-Administration 2007](#)).

Analyses of secondary and exploratory endpoints will be provided in the full SAP.

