**Efficacy Analyses:**

The efficacy analysis will be conducted on the Safety Analysis Set - patients with at least 6 months of treatment from the first dose of selpercatinib. These analyses will be summarized per tumor indication, including patients from both the Phase 1 and Phase 2 portions. A Statistical Analysis Plan (SAP) will provide specific details on the efficacy analysis set.

ORR will be estimated for tumor indication based on the observed proportion of patients whose best overall response, based on RECIST 1.1 or RANO, is confirmed CR or PR as determined by IRC and by the treating Investigator. The estimates of the ORR will be accompanied by a 2-sided 95% confidence interval (CI). Waterfall plots will be used to depict graphically the maximum decrease from baseline in the sum of longest diameters of target lesions. The duration of objective response, PFS, and OS will be summarized descriptively for each cohort using the Kaplan-Meier method.

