2.2. Efficacy Analysis Set

Patients who received at least 1 dose of selpercatinib and achieved at least 6 months of potential follow-up time from the first dose of selpercatinib (or disease progression or death, whichever occurred first), as of a data cutoff, will be considered eligible for efficacy analyses. The efficacy analysis sets are defined by tumor diagnosis and line of therapy and described in [Table JZJA.2.2](#).

Table JZJA.2.2. Description of efficacy Analysis Sets

Tumor Diagnosis/Line of Therapy	Analysis Set	Analysis Set Description
RET fusion-positive NSCLC	Patients Previously Treated with Platinum-Based Chemotherapy	Efficacy eligible patients with RET fusion-positive NSCLC previously treated with platinum-based chemotherapy.
	Treatment-Naïve Patients	Efficacy eligible treatment-naïve patients with RET fusion-positive NSCLC.

Tumor Diagnosis/Line of Therapy	Analysis Set	Analysis Set Description
	Patients Previously Treated with Other Systemic Therapy	Efficacy eligible patients with RET fusion-positive NSCLC previously treated with systemic therapies other than platinum-based chemotherapy.
	Patients with Non-measurable disease	Efficacy eligible patients with RET fusion-positive NSCLC previously treated and treatment-naïve patients without measurable disease by RECIST v1.1.
	CNS Response Analysis Set	Efficacy eligible patients with RET fusion-positive NSCLC who had investigator-identified CNS metastases at baseline (reported as target or nontarget lesion per RECIST v1.1).
RET mutant MTC	Patients Not Previously Treated with Cabozantinib and/or Vandetanib	Efficacy eligible patients with RET -mutant MTC that have had no prior systemic therapy or have been treated with a prior systemic therapy besides cabozantinib and vandetanib.
	Patients Previously Treated with Cabozantinib and/or Vandetanib	Efficacy eligible patients with RET -mutant MTC treated with cabozantinib and/or vandetanib.
	Patients with Non-Measurable Disease	Efficacy eligible patients with RET -mutant MTC previously treated and treatment naïve patients without measurable disease by RECIST v1.1
	Patients Naïve to Any Systemic Therapy	This analysis set is a subset of the ‘Patients Not Previously Treated with Cabozantinib and/or Vandetanib’ analysis set

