	Patients Naïve to Cabozantinib and Vandetanib But Previously Treated with Other Systemic Therapy	This analysis set is a subset of the ‘Patients Not Previously Treated with Cabozantinib and/or Vandetanib’ analysis set
RET fusion-positive thyroid	Patients Not Previously Treated with systemic therapy other than RAI	Efficacy eligible patients with RET fusion-positive TC that have had no prior systemic therapy (lenvatinib, sorafenib) other than RAI
	Patients Previously Treated with systemic therapy other than RAI	Efficacy eligible patients with RET fusion-positive TC previously treated with systemic therapy (lenvatinib, sorafenib) other than RAI
RET mutant non-MTC ^a	Patients with RET mutant non-MTC	Efficacy eligible patients with RET mutant non-MTC
Prior RET inhibitor ^{a,b}	Patients who have received prior treatment with a selective RET inhibitor	Efficacy eligible patients with a prior selective RET inhibitor

Abbreviations: CNS = central nervous system; MTC = medullary thyroid cancer; NSCLC = non-small cell lung cancer; RAI = radioactive iodine; RECIST = Response Evaluation Criteria in Solid Tumours; *RET* = Rearranged during Transfection; TC = thyroid cancer.

^a Selected efficacy analysis will be performed.

^b This group includes patients with *RET* fusion NSCLC, *RET* fusion thyroid, and *RET* mutant MTC and is excluded from the other efficacy analysis sets.

3. Data Cutoff

A data cutoff date will be announced when prespecified requirement in population of patients with *RET* fusion-positive thyroid is met.

Among at least 50 *RET* fusion-positive thyroid cancer who have received radioactive iodine (if appropriate for their tumor histology), all responding patients have been followed for 12 months following onset of response by investigator assessment or until disease progression, whichever comes first.

4. Statistical Analyses

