4.7. Changes to Protocol-Planned Analyses

Efficacy analyses will be performed by proposed indication instead of protocol-defined cohorts.

5. Supporting Documentation

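### Protocol and SAP define different efficacy sets, each partly selected on outcome; the operative SAP rule is only slightly biased, but one calendar rule should replace both

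*Protocol*

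**What the plan says.** **Protocol.** Section 8.5.3 bases efficacy on the "Safety Analysis Set of patients with at least 6 months of treatment from the first dose of selpercatinib". The Synopsis repeats the rule as "Safety Analysis Set - patients with at least 6 months of treatment from the first dose of selpercatinib". Both places then hand over: "A Statistical Analysis Plan (SAP) will provide specific details on the efficacy analysis set".

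**SAP.** Section 2.2 requires at least one dose. It further asks, at the data cutoff, that the patient has "achieved at least 6 months of potential follow-up time from the first dose of selpercatinib (or disease progression or death, whichever occurred first". Section 4.7, which lists changes to protocol-planned analyses, has one entry: "Efficacy analyses will be performed by proposed indication instead of protocol-defined cohorts". The move from time on treatment to potential follow-up is not there.

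**Related text.** Protocol Section 6.4 says that "the Investigator and/or the Sponsor should remove a patient from treatment for any of the reasons listed below", and the reasons include progression, unacceptable toxicity and death. SAP Section 3 sets the cutoff by the thyroid population, once "all responding patients have been followed for 12 months following onset of response by investigator assessment or until disease progression, whichever comes first".

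**The concern.** The efficacy set is the denominator of the primary ORR and the population for PFS and OS, all counted from the first dose. Membership should be fixed by facts known at the first dose or by the calendar.

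Time on treatment is neither. A patient who stops early for progression, toxicity or death drops out of the set under the protocol's words, and such patients are mostly non-responders. The SAP's potential follow-up is a calendar quantity, but the bracket brings outcome back for patients dosed shortly before the cutoff: those who have failed are in, and those dosed on the same day who are responding or stable are out. The two distortions run in opposite directions. A reader following the protocol and a reader following the SAP could report different ORRs from the same data.

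**Working it through.** **1. The plan's own figure.** Protocol Section 8.3 gives Cohort 1 85% power with N = 55 (true ORR 50%, lower limit of the two-sided 95% exact CI above 30%). The smallest qualifying count is 24/55 (lower limit 30.3%; 23/55 gives 28.7%). P(X >= 24) is 86.0% at ORR 50% and 2.2% at 30%. Cohort 4 has the same design; Cohort 2 (29/59) gives 84.9% and Cohort 3 (25/83) 85.3%. The stated power reproduces and is not in dispute.

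**2. Who is in each set.**

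| Patient | Protocol, literal | SAP 2.2 | Calendar rule |
|---|---|---|---|
| First dose >= 6 months before cutoff, treated >= 6 months | in | in | in |
| First dose >= 6 months before cutoff, stopped earlier for any reason | **out** | in | in |
| First dose < 6 months before cutoff, progressed or dead | out | **in** | out |
| First dose < 6 months before cutoff, responding or stable | out | out | out |

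The documents give no early-stopping rates, PFS or share dosed late, so everything below rests on assumed ranges.

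**3. Protocol wording, literal.** With a share d stopping before six months and ORR_d among them, reported ORR = (ORR - d x ORR_d)/(1 - d). For a true ORR of 50%:
- d = 15%, ORR_d = 15%: (0.50 - 0.0225)/0.85 = 56%
- d = 25%, ORR_d = 5%: (0.50 - 0.0125)/0.75 = 65%
- d = 35%, ORR_d = 5%: (0.50 - 0.0175)/0.65 = 74%

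For the decision, take a true ORR of 30%, with 5% of responders and 25% of non-responders stopping early. Reported ORR is 0.285/(0.285 + 0.525) = 35.2%, and the chance that 55 analysed patients clear the 30% bound rises from 2.2% to 12%. With 50% of non-responders stopping, it is 0.285/(0.285 + 0.350) = 44.9%, and the chance is 62%. If both groups stop at the same rate, ORR is unbiased.

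Everyone in such a set is alive at six months, so six-month OS is 100%. If treatment also ended at progression, six-month PFS would be 100%, and under exponential PFS the median would rise by about six months (12 to 18).

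**4. SAP rule.** Let f be the share of treated patients first dosed within six months of cutoff. With uniform entry over that window and exponential PFS (lambda = ln 2/median), the share of them already failed is p = 1 - (1 - exp(-6 lambda))/(6 lambda). They form w = fp/(1 - f + fp) of the set. If none of them responded (worst case), a true ORR of 50% becomes 0.50(1 - w):

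| Median PFS | p | f = 5% | f = 10% | f = 20% |
|---|---|---|---|---|
| 7 months | 24.6% | 49.4% | 48.7% | 47.1% |
| 12 months | 15.5% | 49.6% | 49.2% | 48.1% |
| 24 months | 8.2% | 49.8% | 49.6% | 49.0% |

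At a median of 7 months, Cohort 1 power falls from 86.0% to 81.1% (f = 10%) and 74.1% (f = 20%).

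All patients admitted by the bracket have failed by six months, so six-month PFS becomes (1 - w) x S(6). The loss is w x S(6): 0.0579 x 0.552 = 3.2 points at the worst corner (median 7, f = 20%), and 0.0043 x 0.841 = 0.4 points at the mildest. In simulation, median PFS fell by 0.13 months (median 7, f = 5%) to 0.70 months (24.03 to 23.33 at median 24, f = 20%), and six-month OS by under 1.3 points. With f = 0 every loss is zero.

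These figures treat progression as seen at once. With scans only at weeks 8, 16 and 24 (1.84, 3.68 and 5.52 months) and a median of 6 months, the share of late entrants known to have progressed is [1.84 x 0.191 + 1.84 x 0.346 + 0.48 x 0.471]/6 = 20%, against 28% from the formula. Deaths and optional week-4 scans would raise it somewhat.

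**5. Calendar rule.** In a simulation of 400,000 patients, a set defined by first-dose date alone matched the all-treated PFS and OS curves to within 0.001 at 6 and 12 months. At N = 55, Cohort 1 keeps 86.0% power and 2.2% one-sided error.

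**The case against.** The best defence is that the protocol's words do not govern. Synopsis and Section 8.5.3 both leave the details of the set to the SAP, whose stated purpose includes defining it for the final report. The literal reading also clashes with the protocol's own PFS rules: Section 8.5.3 counts a death before the first planned post-baseline assessment as an event, and that assessment falls at about week 8. Nobody with six months of treatment could have such a death. Progression alone need not end treatment either, since Section 6.4 allows continuation with sponsor approval. Loose wording for follow-up is the likelier explanation.

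On the SAP side, few patients may enter through the bracket. SAP Section 2.1 sends the population still enrolling to a separate report, the cutoff waits for follow-up of thyroid responders, and the protocol's amendment history records a decision to end enrolment to most populations. SAP Section 4.1 also lets changes that do not touch a principal feature be described in the CSR.

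Most of this stands, and it rules out the claim of large bias. Three things survive. The treatment wording appears twice in the current protocol, and a deferral for details does not obviously cover replacing the inclusion rule. The cutoff trigger concerns thyroid responders only, and no enrolment dates are given, so f = 0 cannot be confirmed for the other sets, including the prior-RET-inhibitor and RET-mutant non-MTC sets. And the bracket does no useful work: patients dosed at least six months before cutoff qualify without it.

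**Conclusion.** The documents contradict each other on the primary-endpoint denominator, and SAP 4.7 does not say so. This should be fixed, but it is not evidence that the reported results will be materially wrong.

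A reader might infer that ORR will be inflated and six-month OS fixed at 100%. That needs the SAP to be ignored; the 56-74% range describes the literal protocol wording under assumed stopping rates. A reader might also take the SAP to exclude early non-progressors in general. It does not: everyone first dosed at least six months before cutoff is in, whatever the outcome.

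Under the operative SAP rule the bias is downward, against the drug, and small. A true ORR of 50% falls at worst to about 47-50% for f of 5-20% and median PFS of 7-24 months, all assumed. It is zero if nobody was dosed in the window. No bias in DOR is shown; DOR is computed in responders only.

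**What to change.** Use one rule in the Synopsis, protocol Section 8.5.3 and SAP Section 2.2: all treated patients whose first dose was at least six months before the data cutoff, regardless of treatment duration, progression or death. In the protocol, replace the condition on treatment with this one. In SAP 2.2, delete the bracket on progression or death. In SAP 4.7, list the change from the protocol.

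It would also help to report how many patients in each set were first dosed within six months of cutoff, and to add an all-treated sensitivity analysis of ORR, PFS and OS.

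The cost is wording in two documents and a one-line change to the set derivation. Any patients admitted only through the bracket leave the set; if there are none, no result changes.
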